6.3 Randomization and Blinding

6.3.1 Blinding Method

This section is not applicable as this is an open-label study.

6.3.2 Assignment and Allocation

6.3.2.1 Subject Number

Subjects will be assigned a subject number at study entry (i.e., signing the ICF). The subject numbers will be sequential and rising.

The subject number will comprise of a 5 digit clinical unit number and 5 digit screening number.

6.3.2.2 Randomization Number

Subjects will be randomized in a 2:1 ratio to 50 mg mirabegron and 25 mg mirabegron using a computer-generated randomization Interactive Web Response System (IWRS). All consented subjects who meet the eligibility criteria will be randomized through IWRS. This service is set up prior to the study to allow the sites real-time allocation of the treatment to the next eligible subject based on the specifications and algorithm provided in the Randomization Document.

At visit 2/week 0 (baseline), subjects will be assigned a randomization number in accordance with the randomization code generated by the sponsor's designee.

6.3.2.3 Subject Replacement

An enrolled subject who withdraws or discontinues before dosing or before randomization will be considered a screen failure. Randomized subjects who withdraw or discontinue will not be replaced.

6.4 Investigational Product Compliance

Subject compliance with IP will be assessed at each visit. Compliance will be assessed by counting returned tablets. Deviations from the prescribed dose regimen will be recorded.

If compliance is less than 80%, the investigator or designee is to counsel the subject and ensure steps are taken to improve compliance.

6.5 **Dose Modification**

For 25 mg mirabegron group, a dose escalation to 50 mg is permitted on visit 3 and visit 4, according to investigators' discretion.

6.6 Continued Access to Investigational Product After the End of the Study

Mirabegron has been approved and commercially available in China.

6.7 Treatment of Overdose

Mirabegron administered at single doses up to 400 mg or at multiple doses up to 300 mg daily for 10 days cause overdose. Treatment for overdose should be symptomatic and supportive. In the event of overdose, pulse rate, blood pressure and ECG monitoring are recommended.

6.8 Concomitant Therapy

Subjects are not allowed to use ongoing treatment with any of the following prohibited medications after the start of the washout:

Any medication, other than the IP, used for the treatment of OAB

- Any drugs that are sensitive CYP3A inhibitors, CYP2D6 substrates with a narrow therapeutic index or sensitive P-gp substrates.
- Intradetrusor botulinum toxin injections; except if given > 9 months prior screening and symptoms reappeared comparable to those before botulinum toxin injections.
- Drugs such as α1-AR antagonists, medication for diabetes insipidus (desmopressin, vasopressin), antidepressants ([SSRIs] or tricyclic antidepressants), 5α-reductase inhibitors, capsaicin or resiniferatoxin injections into bladder.
- Nonmedication therapies like chiropractic, physical therapy will also be collected on the nonmedication therapy eCRF.

Subjects are allowed to continue ongoing treatment of α 1-AR antagonists, 5 α -reductase inhibitors (5-ARIs) and Phosphodiesterase type 5 inhibitors (PED-Is) in case of use for Benign Prostatic Hyperplasia (BPH).

Please refer to [Section 10.5 Appendix 5 List of Excluded Concomitant Medications] for drug classes or specific medications that are prohibited during participation in the study.

7 STUDY PROCEDURES AND ASSESSMENTS

- Study procedures and their timing are summarized in the Schedule of Assessments [Table 1]. Adherence to the study design requirements, including those specified in the Schedule of Assessments, is essential and required for study conduct. Prospective protocol waivers or exemptions are not allowed.
- Any change, divergence or departure from the study design or procedures identified in the protocol is considered a protocol deviation. All deviations from the protocol are to be recorded.
- Immediate safety concerns should be discussed with the sponsor immediately upon occurrence or awareness to determine if the subject should continue or discontinue study treatment.
- All screening evaluations must be completed and reviewed to confirm that potential subjects meet all eligibility criteria. The investigator will maintain a screening log to record details of all subjects screened and to confirm eligibility or record reasons for screening failure, as applicable.

• Procedures conducted as part of the subject's routine clinical management (e.g., imaging, blood count) and obtained before signing of the ICF may be utilized for screening or baseline purposes provided the procedures met the protocol-specified criteria and were performed within the time frame defined in the Schedule of Assessments [Table 1].

7.1 Efficacy Assessments

7.1.1 Bladder e-Diary

The bladder diary is part of the subject's e-diary which is used to collect micturition frequency, incontinence episodes as well as volume measurements. After a successful visit 1 /week -1 to -2 [screening]), all subjects will start with the completion of a 3-day bladder e-diary recording micturition frequency and incontinence episodes as well as collection of micturition volume over 2 days. The bladder e-diary should be completed over 3 consecutive days, at minimum 3 days, but not more than 7 days, prior to visit 2/week 0 (baseline).

Upon successful completion of the 3-day bladder e-diary, subject should return for visit 2/week 0 as soon as possible, and no more than 7 days after the start of the diary completion. The completed e-diary data should be reviewed by the investigator, discussed and confirmed with the subject at the start of visit 2/week 0. Upon confirmation of eligibility criteria, the subject shall proceed to randomization. If the investigator is under the impression that the subject is not able to perform all the required assessments and to complete all required forms with credible data, this subject should not be considered for randomization.

After successful randomization, subsequent bladder e-diaries will be completed by the subject over 3 consecutive days in the week prior to visit 3/week 4, visit 4/week 8 and visit 5/week 12. Completion of the 3-day bladder diaries should start at minimum, 3 days (but not more than 7 days) prior to the indicated visit.

7.2 Safety Assessments

Study procedures and their timing are summarized in the Schedule of Assessments [Table 1]. Protocol waivers or exemptions are not allowed.

7.2.1 Laboratory Assessments

Clinical laboratory tests will be performed at a local laboratory.

Blood samples will be collected via a peripherally placed intravenous cannula or by direct venipuncture in a suitable forearm vein.

Blood samples for hematology and biochemistry and urine samples for urinalysis will be collected as indicated in the Schedule of Assessments [Table 1]. The clinical laboratory tests to be performed in the study are listed in [Section 10.6 Appendix 6 Laboratory Assessments].

A blood sample will be collected for serology tests (HAV antibodies [IgM], HBc antibodies, HBsAg, HCV antibodies, syphilis and antibodies to HIV) at screening only.

Urine pregnancy tests (female subjects only) will be performed according to the clinical site's preferred method. Pregnancy tests will be performed as indicated in the Schedule of Assessments [Table 1].

If any of the clinical laboratory tests results be outside the normal range at any scheduled time point during the study, the investigator may decide to repeat the test(s) on new samples. The clinical relevance of the abnormal results will be documented. Clinically relevant changes will be recorded as AEs (see [Section 7.3 Adverse Events and Other Safety Aspects]).

7.2.2 Vital Signs

Blood pressure (SBP and DBP), pulse measurements, and body temperature will be taken as indicated in the Schedule of Assessments [Table 1]. Single measurements of blood pressure and pulse will be measured in the sitting position (when possible, otherwise supine, but always in the same position). Subject should have been calm and without distress for at least 5 minutes. Preferably, the right arm should be used to measure vital signs. Body temperature will be measured with an ear thermometer. These measurements will be used to assess eligibility.

7.2.3 Physical Examination

Physical examination will be performed as indicated in the Schedule of Assessments [Table 1] and whenever there is a medical indication.

The investigator should perform physical examinations in accordance with routine procedures. Any abnormal finding observed at screening must be assessed and documented as not clinically significant if a subject is to be enrolled in the study. After IP administration, new clinically significant findings or a worsening of an ongoing clinically significant abnormal condition will be recorded as an AE (see [Section 7.3 Adverse Events and Other Safety Aspects]).

7.2.4 Electrocardiogram

Routine 12-lead ECGs will be taken as indicated in the Schedule of Assessments [Table 1]. Routine 12-lead ECGs will be taken after the subject has been resting in the supine position for at least 5 minutes. Routine 12-lead ECGs will be taken as single measurements.

The investigator will review, sign and date the ECG after recording to ensure subject safety. The time of the ECG, the interval measurements, as well as an overall conclusion, will be documented. This overall conclusion will be recorded as normal, abnormal not clinically significant, or abnormal clinically significant. If the overall conclusion is abnormal, the details must be recorded.

Per time point, the ECG will be stored electronically and reviewed in a timely manner by the investigator. The electronic data file with all generated ECG variables and electronic files with the digitized tracings will be transferred to the sponsor at the end of the study.

7.2.5 Post Void Residual Volume Assessments

PVR volume will be assessed by ultrasonography at visit 1/week -1 to -2 (screening) and visit 5/week 12 (EoT). The same method should be used for the same subject through the screening and the treatment period. The bladder should only be emptied when it was initially filled with preferably > 50% of the bladder capacity. Every attempt should be made to measure PVR volume within a minute of voiding. A PVR volume of < 100 mL is sufficient and the assessment does not have to be repeated. If the PVR volume is \geq 100 mL, the PVR volume assessment should be repeated (filled with preferably > 50% of the bladder capacity). If the subject is unable to complete a second measurement, it is up to the investigator to judge whether it can be skipped (and write the reason in the eCRF). The lowest PVR volume result measured should be used to evaluate the exclusion criterion. In case the lowest PVR volume measured is \geq 100 mL at visit 1/week -1 to -2 (screening), the subject should be excluded from the study.

7.2.6 **Overactive Bladder Symptom Score**

The OABSS, an assessment tool which has been found to be reliable and valid and highly responsive to treatment related fluctuations in OAB will be performed at visit 2/week 0 (baseline), visit 3/week 4, visit 4/week 8 and visit 5/week 12 (EoT) [Urology; 2006]. Repeating the test after treatment interval is an effective way to assess the efficacy of a mirabegron treatment on OAB symptoms. The OABSS questionnaire is designed to quantify OAB symptoms experienced in the previous week as a single score, and contains questions that address 4 symptoms of overactive bladder:

- Daytime frequency,
- Nighttime frequency,
- Urgency,
- Urge incontinence.

The OABSS has a maximum score of 15 with more weight assigned to urgency and urgency incontinence than on frequency, (see [Section 10.7 Appendix 7 Overactive Bladder Symptom Score questionnaire]).

Questionnaires to be completed by the subject in the local language and provided via the e-diary. Results will be directly entered in the e-diary by the subject.

7.2.7 **Order of Assessments**

The following sequence order will be in effect when more than 1 assessment is required at a time point: routine 12-lead ECG, vital signs, and samples for safety laboratories.

7.3 Adverse Events and Other Safety Aspects

The definitions of an AE or SAE can be found in [Sections 10.3.1 Definition of Adverse Events and 10.3.2 Definition of Serious Adverse Events], respectively.

AEs will be reported by the subject.

The investigator and any qualified designees are responsible for detecting, documenting and recording events that meet the definition of an AE or SAE and remain responsible for following up AEs that are serious, considered related to the study IP, or that caused the subject to discontinue the IP and/or study [Section 10.3 Appendix 3 Adverse Events: Definitions and Procedures for Recording, Evaluating, Follow-up and Reporting].

The method of recording, evaluating, and assessing causality of AE and SAE and the procedures for completing and transmitting SAE reports are provided in [Section 10.3 Appendix 3 Adverse Events: Definitions and Procedures for Recording, Evaluating, Follow-up and Reporting].

7.3.1 Time Period and Frequency for Collecting Adverse Event and Serious Adverse Event Information

All SAEs will be collected from the signing of the ICF until 30 days after the final IP administration or when the subject is determined to be a screen failure and reported in the eCRF.

All AEs will be collected from the signing of the ICF until 30 days after the final IP administration or when the subject is determined to be a screen failure and reported in the eCRF.

If the severity of an SAE/AE changes, the event should be relisted in the eCRF with the new severity and new onset date.

If the severity decreases, the SAE/AE should be relisted in the eCRF with the new severity and new onset date. The exception is ongoing pre-dose events that continue post-dose and improve post-dose. Such events should not be re-listed.

If the severity of an SAE reduces, the details of the AE should be provided on the SAE worksheet for the medical assessor to be able to assess the course of the event.

All SAEs will be recorded and reported to the sponsor or designee immediately and under no circumstance should this exceed 24 hours, as indicated in [Section 10.3 Appendix 3 Adverse Events: Definitions and Procedures for Recording, Evaluating, Follow-up and Reporting]. The investigator will submit any updated SAE data to the sponsor within 24 hours of it being available.

Investigators are not obligated to actively seek AE or SAE after conclusion of the study participation. However, if the investigator learns of any SAE, including a death, at any time after a subject has been discharged from the study, and he/she considers the event to be reasonably related to the study IP or study participation, the investigator must promptly notify the sponsor.

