### 5.4.1 Adverse Events

AEs will be coded using MedDRA. A TEAE is defined as an AE observed after starting administration of the IP until 30 days after the final administration of IP. If the adverse event occurs on Day 1 and the onset check box on the (AE) eCRF is marked "Onset after first dose of study drug" or the onset check box is left blank, then the adverse event will be considered treatment emergent. If the adverse event occurs on Day 1 and the onset check box is marked "Onset before first dose of study drug", then the adverse event will not be considered treatment emergent. If a subject experiences an event both during the pre-investigational period and during the investigational period, the event will be considered as TEAE only if it has worsened in severity (i.e., it is reported with a new start date).

A drug-related TEAE is defined as any TEAE with at least possible relationship to study treatment as assessed by the investigator or with missing assessment of the causal relationship.

AEs may be upgraded by the sponsor according to the Important Medical Event process.

A drug-related TEAE is defined as any TEAE with at least a possible relationship to study treatment as assessed by the investigator or with a missing assessment of the causal relationship.

Common TEAEs are defined as preferred terms (PTs) that have been reported by at least 5% of the subjects, in any treatment group.

When an AE start or stop date is missing, the date will be imputed using the rules in Section 6.10.2.2.

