### 6.5.1 Adverse Events

Summaries and listings of SAEs and Serious TEAEs include SAEs upgraded by the sponsor based on review of the Sponsor's list of Always Serious terms or upgraded according to the Important Medical Event process, if any upgrade was done.

The coding dictionary for this study will be MedDRA. It will be used to summarize AEs by System Organ Class (SOC) and Preferred Term (PT).

An overview table will include the following details:

- Number of TEAEs,
- Number and percentage of subjects with TEAEs,
- Number of drug related TEAEs,
- Number and percentage of subjects with drug related TEAEs,
- Number of serious TEAEs,
- Number and percentage of subjects with serious TEAEs,
- Number of serious drug related TEAEs,
- Number and percentage of subjects with serious drug related TEAEs,
- Number of TEAEs leading to withdrawal of treatment,
- Number and percentage of subjects with TEAEs leading to withdrawal of treatment,
- Number of drug-related TEAEs leading to withdrawal of treatment,
- Number and percentage of subjects with drug-related TEAEs leading to withdrawal of treatment,
- Number of TEAEs leading to death,
- Number and percentage of subjects with TEAEs leading to death,
- Number of drug-related TEAEs leading the death,
- Number and percentage of subjects with drug-related TEAEs leading to death, and
- Number and percentage of subjects who died.

The number and percentage of subjects with TEAEs, as classified by SOC and PT will be summarized for each treatment group. Summaries will be provided for:

- TEAEs,
- Drug related TEAEs,
- Serious TEAEs,
- Drug related serious TEAEs,
- TEAEs leading to withdrawal of treatment,
- Drug related TEAEs leading to withdrawal of treatment,
- Frequently Reported (>=5% in Any Treatment Group) TEAEs Excluding SAEs

The number and percentage of subjects with TEAEs, as classified by PT only, will be summarized for each treatment group.

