The number of TEAEs and the number and percentage of subjects with TEAEs, as classified by SOC and PT will also be summarized by severity and by relationship to study drug. In the subject count, if a subject has multiple TEAEs with the same SOC or PT, but with differing severity or relationship, then the subject will be counted only once with the worst severity and highest degree of relationship, however, if any of the severity or relationship values are missing then the subject will be counted only once with missing severity or relationship. In the adverse event count, the adverse events will be presented in each category they were classified to. Drug related TEAEs will be presented in a similar way by severity only.

Adverse events of interest will be tabulated by PT.

AEs will be provided in listing format by site and subject for the SAF.

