#### 6.10.2 Imputation Rules for Incomplete Dates

As a general principle, no imputation of missing data for variables will be done. Exceptions are the start and stop dates of AEs and concomitant medication. The imputed dates will be used to allocate the concomitant medication and AEs to a treatment group, in addition to

determining whether an AE is/is not treatment emergent. Listings of the AEs and concomitant medications will present the actual partial dates; imputed dates will not be shown.

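### Adverse events that improve on treatment are relisted with a new onset date and never linked, so TEAE counts rise and, if allocation is by date, a 25 mg event can appear as new under 50 mg

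*Protocol*

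**What the plan says.** **Recording.** Protocol 7.3.1 opens a new record at any change of grade: "If the severity of an SAE/AE changes, the event should be relisted in the eCRF with the new severity and new onset date". It then repeats the instruction for improvement: "If the severity decreases, the SAE/AE should be relisted in the eCRF with the new severity and new onset date". One case is exempt: "The exception is ongoing pre-dose events that continue post-dose and improve post-dose".

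**Definition.** SAP 5.4.1 states: "A TEAE is defined as an AE observed after starting administration of the IP until 30 days after the final administration of IP". It adds a worsening condition for events seen both before and after dosing began. It has no such condition for the switch from 25 mg to 50 mg, and neither document joins relisted records into one episode.

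**Counting.** The overview table in SAP 6.5.1 has event rows, starting with "Number of TEAEs", beside the subject rows. For subjects, SAP 6.5.1 counts each person once per system organ class or preferred term at the worst severity. Protocol 9.4.3.1 likewise takes the worst severity when the same event is recorded more than once.

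**Columns.** SAP 6.5 shows 25 mg (never up-titrated, later up-titrated, total), 50 mg (as randomized, up-titrated from 25 mg, total) and total mirabegron. The last is the sum of 25 mg total and 50 mg as randomized. On allocation, SAP 6.10.2 says of incomplete dates: "The imputed dates will be used to allocate the concomitant medication and AEs to a treatment group".

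**The concern.** The recording rule produces one record per severity grade, and the counting rules treat a record as an event. Two consequences follow.

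- An event that resolves in steps contributes more to the TEAE total than one that stays at a single grade until it stops. The event rows then partly measure how many grade changes were recorded.
- A subject who escalates is followed in two dose columns. If the onset date decides the column, a resolving 25 mg event gets a fresh onset date after the switch and is reported as emerging on 50 mg.

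Safety is a secondary objective, and the study is meant to inform licence renewal and the choice of starting dose in Chinese patients. A table that credits the higher dose with events begun on the lower one misdescribes what happens after escalation.

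**Working it through.** The plan states no figure on this point, so there is none to reproduce. The check follows one event through the rules and then works out the weight of one subject.

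**1. Event count for one episode.** Take an event with onset after first dose that goes from severe to moderate to mild. Protocol 7.3.1 gives one record at onset and one at each of two improvements: 1 + 2 = 3 records. All three fall in the TEAE window of SAP 5.4.1, so the overview event row rises by 3 for a single episode.

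**2. Trace across the dose switch.** The dosing dates come from the worked exposure example in SAP 5.5.1: 25 mg from 1 July 2020 and 50 mg from 29 July 2020. Assume an event that is moderate from 20 July and eases to mild on 31 July.

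| Record | Onset | Severity | TEAE | Dose at onset |
|---|---|---|---|---|
| 1 | 20 July | moderate | yes | 25 mg |
| 2 | 31 July | mild | yes | 50 mg, up-titrated |

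With allocation by onset date, the episode yields 2 events, one in each dose column. The subject is counted once under 25 mg and once under 50 mg up-titrated, and therefore also under 50 mg total. With linked records it would yield 1 event on 25 mg and 0 on 50 mg.

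**3. Weight of one carried-over subject.** The 50 mg arm has about 166 subjects (Protocol 9.2) out of 249, which leaves 249 − 166 = 83 on 25 mg. Let U be the number who escalate. The documents do not give U, so the values below are assumptions: 20, about half of 83, and all 83. All randomized subjects are taken as treated. For one preferred term, the added percentage is 100/U in the up-titrated column and 100/(166 + U) in 50 mg total.

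| U (assumed) | Up-titrated column | 50 mg total |
|---|---|---|
| 20 | 100/20 = 5.0 points | 100/186 = 0.54 points |
| 41 | 100/41 = 2.4 points | 100/207 = 0.48 points |
| 83 | 100/83 = 1.2 points | 100/249 = 0.40 points |

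SAP 5.4.1 calls a preferred term common at 5% of subjects in any treatment group. If the up-titrated column counts as a treatment group, one carried-over subject is enough when U is 20 or fewer.

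**4. Where it cannot occur.** Subjects randomized to 50 mg never took 25 mg in the study, so the as-randomized column receives no carry-over. Total mirabegron does not add in the up-titrated column, so carry-over leaves its subject counts unchanged.

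**The case against.** The strongest reply is that most of the safety output is unaffected. Within a column, the count-once, worst-severity rule protects subject numbers and percentages. Protocol 4.3 gives the primary efficacy and safety role to the 50 mg group and calls the 25 mg group exploratory. The summaries are descriptive, and the listings by subject would let a reader see such sequences. All of that stands and limits the size of the point. It does not correct the event rows, and it does not stop one episode from placing a subject in two dose columns.

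Three stronger readings are tempting, and the documents do not support them.

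- A reader might infer that the SAP mistakes every new start date for worsening, because it says "the event will be considered as TEAE only if it has worsened in severity (i.e., it is reported with a new start date". That sentence covers only events already present before the investigational period. Those are the events that Protocol 7.3.1 exempts from relisting when they improve. For them a new start date after dosing normally does mean worsening, so the two documents agree there.
- A reader might take "In the adverse event count, the adverse events will be presented in each category they were classified to" as the definition of the overview count. It belongs to the tables by severity and relationship, where showing each record in its own category is intended. The inflation follows from the absence of any linking rule.
- A reader might treat allocation by onset date as stated. SAP 6.10.2 says only that imputed dates serve for allocation, and no sentence covers complete dates. With dose-split columns and no other rule given, allocation by date is a reasonable inference, but it remains one.

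**Conclusion.** The point holds in limited form and is minor. The repeated counting in the event rows follows directly from the text: an improving post-dose episode counts once per recorded grade. The misplacement under 50 mg rests on the inferred date allocation. It needs an event that starts on 25 mg, is still present at escalation and then drops a grade, in a subject not already counted for that term on 50 mg.

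The 5.0, 2.4 and 1.2 points are the weight of one subject at assumed values of U. They do not estimate bias, because the documents give neither U nor the frequency of such events. The subject-level effect is confined to the 50 mg up-titrated column and, at about 0.4 to 0.5 points per subject, 50 mg total. It would be wrong to conclude that TEAE incidence is inflated throughout.

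**What to change.** Change the counting rules in SAP 5.4.1 and 6.5.1 only:

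1. Link contiguous records of the same event in one subject into one episode.
2. Count the linked episode once in event counts, at its worst severity within the dose column.
3. Allocate it to the dose being taken at its first treatment-emergent onset, and say that this applies to complete as well as imputed dates.
4. Count it under 50 mg up-titrated only if it starts or worsens after the switch.
5. Keep the existing rule that a pre-dose event that worsens after first dose is a TEAE. Dating every linked episode from its very first onset would wrongly remove these events, which is why item 3 refers to the first treatment-emergent onset.

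The relisting instruction in Protocol 7.3.1 and the data collected stay as they are. The cost is SAP wording, which SAP section 1 allows up to hard lock, and a record-linking step in the adverse event programming.
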